4.0 SUMMARY OF CHANGES

This section describes the changes in reference to the SAP Incorporating Amendment No. 1.

The primary purpose of this amendment is to revise the definition of the event time of a Cognitive Impairment Adjudication Committee (CIAC) CIAC confirmed event of MCI due to AD and provide additional analyses for the efficacy futility analysis. The following is a summary of the changes made in the amendment. Detailed description of amendments to the text is presented in [Appendix E](#).

1. The definition of the event time of a CIAC-adjudicated event of MCI due to AD has been revised as the time from a subject's randomization date to the date of the first **scheduled visit** of the two consecutive **scheduled visits** at which that subject was assessed with a clinical diagnosis and determined as an primary endpoint event by CIAC using the data from scheduled visit and the triggered unscheduled comprehensive medical follow up visits.

Justification: This change will reflect the thinking that, in any subject dossier reviewed by the CIAC, the first scheduled visit is the first of the 4 visits considered by CIAC in their adjudication of primary endpoint event, and it represents the first time point of these 4 visits where clinical impairment or cognitive decline is first noted. This revised definition better reflects the concept of "**time to onset**" of the MCI due to AD – "onset" meaning start of symptoms that are confirmed as MCI due to AD (or AD dementia) by the CIAC.

2. The data collected at the EOS/EW visit is allowed to be used to determine the primary efficacy events of MCI due to AD.

Justification: the data collected at the EOS/EW is similar to those planned at the unscheduled CMFV.

3. The memory domain score derivation algorithm is revised so that at least one of the CVLT-II episodic memory tests (CVLT-II Short-delay free recall correct or CVLT-II Long-delay free recall correct) is required to be non-missing. The requirement of BMVT-R being non-missing is removed.

Justification: The BVMT-R can be missing for many reasons other than cognition (arthritis, motor issues, examiner error). The requirement of both BVMT and at least one CVLT-II to be non-missing may cause valid data points to be omitted (such as subjects who complete CVLT only). The composite measure becomes uninformative without the memory domain; however, the CVLT alone can be used to calculate a memory domain.

4. Additional summaries and analyses are added to evaluate the biomarker qualification performance. Key secondary endpoints and additional variables (only at the domain and composite score levels) will be summarized and analyzed using the data from placebo subjects who are classified into low and high risk groups.

Justification: These analyses will be helpful for the evaluation of the biomarker qualification performance and will be presented at the end of study.

5. At the time of the efficacy futility analysis, if the conditional power is $<30\%$, the following subgroup analyses will be performed on the primary efficacy endpoint: gender (male vs. female), APOE risk-status (low vs. high) and baseline MMSE (≤ 27 vs. ≥ 28). A particular subgroup analysis (e.g. female) will be performed only when there are at least 20% of the total primary events in the subgroup.

Justification: This addition is expected to be informative in the efficacy futility assessment when the conditional power based on the primary event is $<30\%$.

6. At the time of the efficacy futility analysis, if the conditional power is $<30\%$, the following subgroup summaries and MMRM analyses will be performed on the change from baseline in the composite score, CVLT-II Long and Short Delay Free Recall Correct, BVMT-R Delayed Recall and MMSE total score: gender (male vs. female), APOE risk-status (low vs. high) and baseline MMSE (≤ 27 vs. ≥ 28). The subgroup analysis will be performed only when there are at least 400 subjects in a subgroup.

Justification: This addition is expected to be informative in the efficacy futility assessment when the conditional power based on the primary event is $<30\%$.

7. At the time of the efficacy futility analysis, if the conditional power is $<30\%$, and the treatment effect on the change from baseline by visit in the composite score is statistically significant ($p\text{-value} < 0.05$), a joint model of the time-to-event data and the longitudinal composite score data will be fitted to estimate the association between the composite score and hazard rate of MCI due to AD over time during the treatment period. Details of this model are presented in Section 9.16.

Justification: This addition is expected to be informative in the efficacy futility assessment when the conditional power based on the primary event is $<30\%$.

8. At the time of the efficacy futility analysis, if the conditional power is between 10% ($>10\%$) and 30% ($<30\%$), the “progression” of the conditional power in terms of an increasing number of the events vs. total needed will be provided for the following information fractions: 10% (20 events), 20% (41 events) and 34% (69 events). The events will be selected based on the time of the occurrence of the event relative to the first dose.

Justification: When the evidence against the null hypothesis is accumulating, the conditional power should increase as the information fraction increases. However, if the CP does not change as the information fraction increases, it may be unlikely evidence against the null hypothesis is being accumulated. Essentially if CP remains flat across 10%, 20%, 30% of events, it makes it less likely we would reject the null hypothesis at end of study.

5.0 INTRODUCTION

This document describes the statistical analyses to be performed and data presentations to be produced for this phase 3, randomized, double-blind, parallel-group, placebo-controlled study to simultaneously qualify a biomarker algorithm for prognosis of risk of developing mild cognitive impairment due to Alzheimer's Disease (MCI due to AD) and to test the safety and efficacy of pioglitazone (AD-4833 SR 0.8 mg QD) to delay the onset of MCI due to AD in cognitively normal subjects.

The purpose of this statistical analysis plan (SAP) is to ensure the credibility of the study findings by specifying the statistical approaches to the analysis of the double-blind data prior to database lock. This SAP was developed based on the International Conference on Harmonisation (ICH) E3 and E9 Guidelines and in reference to the following documents:

- Protocol AD-4833/TOMM40_301 Amendment #1 dated 09 April 2013.
- Protocol AD-4833/TOMM40_301 Amendment #2 dated 19 March 2014.
- Protocol AD-4833/TOMM40_301 Amendment #3 dated 10 November 2014.
- Protocol AD-4833/TOMM40_301 Amendment #4 (Local-Russia) dated 15 April 2015.
- Protocol AD-4833/TOMM40_301 Amendment #5 dated 24 July 2015.

Any deviations during the analysis and reporting process from the current statistical analysis plan will be described and justified in the final report. Analysis issues that suggest changes to the principal features stated in the protocol will be documented in a protocol amendment. Otherwise, the statistical analysis plan will be updated through an amendment with the changes in the analyses documented in the amendment.

6.0 OBJECTIVES AND STUDY DESIGN

6.1 Primary Objectives

For biomarker risk algorithm qualification:

- To qualify the biomarker risk algorithm composed of TOMM40 rs10524523 genotype, APOE genotype, and age for prognosis of the risk of developing MCI due to AD within 5 years.

For efficacy evaluation of pioglitazone:

- To evaluate the efficacy of pioglitazone compared with placebo to delay the onset of MCI due to AD in cognitively-normal subjects who are at high-risk, as identified by the biomarker risk algorithm at enrollment, for developing MCI due to AD within 5 years.

6.2 Key Secondary Objectives

- To evaluate the effect of pioglitazone compared with placebo on the progression of cognitive decline.
- To evaluate the effect of pioglitazone compared with placebo on functional decline and instrumental activities of daily living.

6.3 Additional Objectives

6.3.1 Safety Objective

- To evaluate long-term safety and tolerability of pioglitazone compared with placebo during the course of the treatment.

6.3.2 Exploratory Objectives

- CCI
-
-
-
-
-

- CCI
-

6.4 Study Design

This phase 3 study is a multicenter, randomized, double-blind, placebo-controlled, parallel-group study designed to pursue two primary objectives independently yet simultaneously: (1) to qualify a biomarker risk algorithm composed of TOMM40 rs10524523 genotype, APOE genotype, and age for prognosis of the risk of developing MCI due to AD and (2) to evaluate the efficacy of pioglitazone (AD-4833 SR 0.8 mg once daily [QD]) to delay the onset of MCI due to AD in cognitively normal subjects who are prognosed to be at high risk of developing MCI due to AD within 5 years.

The study duration will be the time needed to accumulate a total of 202 conversions in non-Hispanic/Latino Caucasian subjects within the high-risk stratum from normal cognition to a diagnosis of MCI due to AD, currently anticipated to be a minimum of 4 years. For the purposes of this study, a Caucasian subject will be defined as a person having origins in any of the original peoples of Europe, the Middle East, or North Africa. Hispanic/Latino will be defined as a person of Cuban, Mexican, Puerto Rican, South or Central American origin, regardless of race. The study will primarily recruit from large community-based populations.

The subjects must be cognitively normal as assessed first by performance on the MMSE at Screening, and then on the CDR scale and the Cognitive Test Battery (Sections 9.1.15.1 and 9.1.15.2 of the protocol) at Baseline (Visit 2). The subject must be between the ages of 65 and 83 years, inclusive, at time of the Screening Visit. The subjects must have a project partner able to complete an Acknowledgement Form on his or her own behalf and take part in the study to provide information on the cognitive, functional, and behavioral status of the subject and to assist with monitoring of study medication, if needed, for as long as the subject is in the study.

Based on statistical requirement, a minimum of 2,793 subjects will be stratified into high- and low-risk (for the development of MCI due to AD over the next 5 years) groups based upon application of the biomarker risk algorithm. Subjects will be randomized via interactive web response system (IWRS) into this study as follows:

[figure not shown]
- Non-Hispanic/Latino Caucasian subjects. A minimum of 2,660 subjects further divided into:
 - Approximately 2,346 subjects in the high-risk group (pioglitazone, n=1,173; placebo, n=1,173).
 - Approximately 314 subjects in the low-risk group: All subjects stratified to the low-risk stratum will also be randomized to maintain the stratification blind, but all subjects in this stratum will receive placebo.

- Non-Caucasian subjects and Hispanic/Latino Caucasian subjects. Subjects will be allocated to risk strata using the same algorithm as for the non-Hispanic/Latino Caucasian subjects.

Since all subjects screened at the time of Amendment 5 will be allowed to randomize if they continue to meet all eligibility criteria, it is estimated that approximately 3,500 will be randomized with the following groups:

- Non-Hispanic/Latino Caucasian subjects. Estimated 3,330 subjects further divided into:
 - Approximately 2,940 subjects in the high-risk group (pioglitazone, n=1,470; placebo, n=1,470).
 - Approximately 394 subjects in the low-risk group: All subjects stratified to the low-risk stratum will also be randomized to maintain the stratification blind, but all subjects in this stratum will receive placebo.
- Non-Caucasian subjects and Hispanic/Latino Caucasian subjects. Subjects will be allocated to risk strata using the same algorithm as for the non-Hispanic/Latino Caucasian subjects (n=167).

Because the data used to develop the biomarker risk algorithm was collected in non-Hispanic/Latino Caucasian subjects only, biomarker qualification will be based upon non-Hispanic/Latino Caucasian subjects in the placebo arm of the high-risk stratum compared to data from non-Hispanic/Latino Caucasian subjects in the low-risk stratum. Likewise, the primary analyses to evaluate the effects of pioglitazone versus placebo will be within the non-Hispanic/Latino Caucasian high-risk sub-group. CCI

An interactive response system will be used for central randomization. Stratification status and treatment assignment of all study participants will be double-blind. The randomization will be stratified based on participation in the vMRI substudy (approximately 300 subjects).

For subjects who are not participating in the vMRI substudy, subjects in the high-risk stratum will be randomized to pioglitazone and placebo in a 1:1 ratio. Subjects in the low-risk stratum will be randomized only to placebo.

For subjects who are participating in the vMRI substudy, subjects in the high-risk stratum will be randomized to pioglitazone and placebo in a 5:4 ratio. Subjects in the low-risk stratum will be randomized only to placebo.

It is estimated that at least 60% of subjects who present for screening will be low-risk as determined by the biomarker risk algorithm. Because the study requires many more high-risk subjects than low-risk subjects to be randomized into the study, a random rejection algorithm for low-risk subjects was implemented in the IWRS. The low-risk rejection algorithm is designed to lengthen the enrollment period for low-risk subjects in such a way that the ratio of high-risk to low-risk subjects randomized into the study is relatively stable over the entire enrollment period.

This will facilitate maintaining double-blinding of risk assignment for all subjects throughout the entire course of the study. Details of the low-risk random rejection algorithm are provided in the AD-4833/TOMM40_301 Study System Requirements document which was authored by the IWRS vendor, Bracket.

Subjects will be instructed to take the first dose of study medication in the morning on the day following the randomization visit.

[figure not shown]
A project partner will be required to participate with the subject in the study visits, including eligibility at Baseline (Visit 2) and follow-up. The project partner is a spouse, adult child, or other person familiar with the participant's health and daily functioning for a minimum of two years prior to the Baseline Visit. Subjects and their project partners are expected to attend study visits every 6 months after randomization, for assessments of safety, efficacy, and treatment compliance. In addition, the subject will be contacted for telephone-based safety checks between visits. In-person participation of the project partner is mandatory at Baseline (Visit 2), comprehensive medical follow-up, and End-of-Study Visits; while in-person participation is also strongly encouraged at all other study visits, telephone assessments for project partners will be acceptable in cases when in-person participation is not possible. If a comprehensive medical follow-up evaluation is needed (see Section 9.1.15 of the protocol) or if a safety issue is suspected, further evaluation of the subject may be required, which may include an unscheduled clinic visit. The project partner should attend unscheduled visits, whenever possible. If the original project partner is not able to continue participation in the study for any reason, he/she may be replaced by a different individual who also meets the criteria described above. The new project partner must sign the acknowledgement form prior to any of the project partner protocol directed procedures being performed.

Two sets of blood samples for deoxyribonucleic acid (DNA) will be collected during the course of this study:

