9.1.4 Grouping of Centers

Pooling of small sites will be done (if necessary) to form centers for purposes of analysis.

Before unblinding the study, sites that are considered small (<40 subjects) will be pooled with geographically similar sites to minimize artifacts in the statistical analyses from imbalances in subject counts within the sites.

Starting with the smallest center, center(s) with fewer than 40 subjects randomized will be pooled into the nearest center. The pooling will start first within each country; if it is still small, other countries within the same geographical region (for example, US, Europe, Rest of World) will also be considered. The pooled centers within a region which still have fewer than 40 subjects will be kept as they are and will not be pooled with centers in other regions.

The pooling of the centers will be reviewed and approved by the clinical and statistical team for agreement, and will then be used in the appropriate analyses once the database has been locked and unblinded.

Quality issues were detected at site 5055; therefore, data collected exclusively at that site will be excluded for purposes of efficacy analyses.

Because of the smaller number of events available at the time of the efficacy futility analysis, pooling will be done for the efficacy futility analysis using a smaller number of pooled centers, based on country/sovereign state, as shown below.

- US
- UK
- Australia
- Switzerland/Germany

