9.9.3.2 Primary efficacy analysis

A similar analysis process as described above for the primary biomarker risk algorithm analysis will be used to compare the placebo- and active-treated non-Hispanic/Latino Caucasian subjects within the high-risk group (ie, using a similar CPH model with covariates of center, gender, and education and an additional covariate of age but using a factor of high-risk treatment group instead of biomarker risk assignment). If this test is significant at the 0.01 level, it can be concluded that active treatment has delayed the development of mild cognitive impairment due to AD.

An exact partial likelihood function will be constructed to fit the Cox proportional hazards (CPH) model to accommodate events with the same times to the event. The robust sandwich estimate for the covariance matrix from the CPH model will be used. The analysis of the primary efficacy comparison will be conducted using the FAS and a CPH model of MCI due to AD events with a factor for treatment and including center, gender, education, and age as covariates.

Parameter estimates, 2-sided 99% CIs, and appropriate p-values for the hazard ratios obtained from the CPH model will be computed to test the null hypothesis of equality of the hazard functions between the high-risk pioglitazone and high-risk placebo treatment groups.

Assessment of the proportional hazards assumption for treatment group will be assessed. Plots of Schoenfeld residuals obtained from the CPH models that fit the primary MCI-to-AD endpoint versus ordered time of events along with a smoothing spline will be used to evaluate the proportional hazards assumption for treatment group. Systematic departures from a horizontal line are indicative of meaningfully non-proportional hazards. Diagnostic checks will be presented in CSR Appendix 16.1.9.

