9.9.3.3 Supportive Nonparametric Interval-Censoring Analyses

Alternative methods of analysis may be considered should some of the underlying model assumptions seem inappropriate (eg, non-proportional hazards). The reasons for any changes to the planned approach and methods will be fully documented.

Most survival analysis methods, including the CPH model, work best when the true event date is known for each and every event which occurs during a study (eg, right censoring). For complex events such as MCI due to AD, generally the true event date is unknown and is only detected at a subsequent visit (ie, interval censoring).

Primary high-risk placebo versus low-risk placebo biomarker analysis

As a sensitivity analysis to the above primary biomarker risk assignment analysis, a nonparametric analysis which accounts for interval censoring by using a weighted generalized log-rank test, stratified by gender, will be done using SAS PROC ICLIFETEST with the option WEIGHT=FINKELSTEIN (which corresponds to a proportional hazards assumption).

Primary high-risk pioglitazone versus placebo efficacy analysis

As above, alternative methods of analysis may be considered if some of the underlying CPH model assumptions are violated; and a similar nonparametric sensitivity analysis using SAS PROC ICLIFETEST will be done to account for interval censoring and its possible effect on the results of the primary efficacy analysis.

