9.9.3.4 Supportive Log-rank Sensitivity Analyses

Primary high-risk placebo versus low-risk placebo biomarker analysis

As a sensitivity analysis to the above primary biomarker risk assignment analysis, a log-rank test, stratified by gender, will be done using SAS PROC LIFETEST.

Primary high-risk pioglitazone versus placebo efficacy analysis

A similar log-rank sensitivity analysis as described above for the primary biomarker risk assignment analysis will be used to compare the placebo- and active-treated non-Hispanic/Latino Caucasian subjects within the high-risk group (ie, stratified by gender, but using a factor of high-risk treatment group instead of biomarker risk assignment category).

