9.9.5 Sensitivity Analyses Using Alternative Event Definitions

As sensitivity analyses for the primary biomarker and primary efficacy analyses, analogous analyses as described in Sections 9.9.3.1 and 9.9.3.2 will be done using the following revised definitions related to an event of MCI due to AD:

- Revised Event Time Definition: For purposes of analysis, the revised **event time** of a CIAC confirmed event of MCI due to AD is the time from either:
 - (1) the randomization date to the **date of the first unscheduled comprehensive medical follow-up visit** which was triggered by the first of the two consecutive scheduled visits at which a subject was assessed with a diagnosis of MCI due to AD (or AD itself) by the CIAC; or
 - (2) the randomization date to the **date of the unscheduled comprehensive medical follow-up visit** which was triggered by the subject's last scheduled visit during the study because the subject was assessed (for the first and only time) with a diagnosis of MCI due to AD (or AD itself) by the CIAC.

The revised event time definition above changes the event time so that it is based on the date of the first unscheduled visit date at which a case of MCI due to AD was determined by CIAC (since CDR data isn't collected at scheduled visits).

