9.9.6 Analysis of Key Secondary Variables

The change from baseline in cognitive battery composite score will be analyzed as a continuous variable by study visit using MMRM (mixed model for repeated measures) analysis of covariance with treatment, gender, center, visit, and treatment-by-visit interaction as fixed, categorical effects and education, age, baseline composite score, and baseline composite score-by-visit as continuous, fixed covariates. The effect at each time point for each treatment is allowed to vary freely, and an unstructured covariance matrix will be used to model the within-subject errors. The Kenward-Roger approximation will be used to estimate denominator degrees of freedom. Based on a Missing at Random (MAR), this analysis will be performed using observed case data only.

The SAS code for the MMRM analysis will be as follows:

```
Proc mixed data=all;
```

- class visit treat center gender subject;
- model Change = Baseline Baseline*visit treat center gender education age visit visit*treat /solution ddfm=KenwardRoger;
- repeated visit/subject=subject type=UN;
- lsmeans visit*treat / cl pdiff.

In the above model, Baseline is the baseline value and Change is the change from baseline value.

Similarly, the change from baseline in ADCS ADL-PI ADL total score will be analyzed as a continuous variable by study visit using MMRM, where the ADCS ADL-PI ADL total score Baseline, gender, education, and age will be used as the covariate adjustments in the MMRM.

Key secondary endpoints will be analyzed (including reporting mean differences, CIs, and p-values) using the FAS subjects in the primary efficacy population (high-risk, non-Hispanic/Latino subjects) using a 0.01 significance level.

Although change-from-baseline endpoints will be assessed at all visits, the primary time frame for purposes of efficacy analysis is the change from baseline to Month 48 (Year 4).

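### The vMRI substudy is a randomisation stratum with its own allocation ratio (5:4 rather than 1:1), but no visible primary, sensitivity or key secondary efficacy model includes it; any bias is small

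*SAP*

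**What the plan says.** SAP 6.4 makes vMRI participation a stratification factor: "The randomization will be stratified based on participation in the vMRI substudy (approximately 300 subjects". It then gives two ratios. Outside the substudy, high-risk subjects are randomised 1:1; inside it, "subjects in the high-risk stratum will be randomized to pioglitazone and placebo in a 5:4 ratio". Protocol Appendix H also gives 5:4. Protocol 6.1 gives 1:1 for the high-risk stratum without mentioning the exception.

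Protocol 8.1.3 also randomises within two race/ethnicity groups, but the primary efficacy population (high-risk, non-Hispanic/Latino Caucasian) lies inside one of them. Within that population, vMRI participation is the only stratum the documents state.

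The efficacy analyses are specified as follows:

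- **Primary Cox model (SAP 9.9.3.2):** "a CPH model of MCI due to AD events with a factor for treatment and including center, gender, education, and age as covariates".
- **Interval-censored analysis (9.9.3.3):** a "weighted generalized log-rank test, stratified by gender, will be done using SAS PROC ICLIFETEST".
- **Log-rank analysis (9.9.3.4):** "a log-rank test, stratified by gender, will be done using SAS PROC LIFETEST".
- **Alternative event times (9.9.5):** "analogous analyses as described in Sections 9.9.3.1 and 9.9.3.2 will be done", so the Cox covariates carry over.
- **Key secondary composite score (9.9.6):** "model Change = Baseline Baseline*visit treat center gender education age visit visit*treat". The sentence on ADCS ADL-PI lists baseline, gender, education and age, and does not repeat center.
- **Futility analysis:** a Cox model, for which "pooling will be done for the efficacy futility analysis using a smaller number of pooled centers" (9.1.4), namely four country groups.

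Participation appears in none of these. It is not a listed subgroup in 9.9.3.5, and SAP 9.17 does not mention the omission. Some SAP text is redacted, so this applies to the visible text.

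**The concern.** When every stratum has the same allocation ratio, leaving a stratification factor out of the model mainly costs precision. Here the ratio differs, so participants are over-represented on pioglitazone by design. If their event rate also differs from that of other subjects, the pooled hazard ratio absorbs part of the difference, and a larger sample does not remove it.

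A difference is possible. Appendix H runs the substudy at selected sites, asks for separate consent and excludes people with an MRI contraindication. The center term in the Cox model and the composite-score model should absorb most between-site differences, but not selection within a site. The log-rank and interval-censored tests have no center term, and at the futility analysis center shrinks to four groups, so less is absorbed there.

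At stake is a small shift, of unknown direction, in the primary hazard ratio and in the statistic that feeds conditional power.

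**Working it through.** **Inputs from the documents.** About 300 participants; ratios 5:4 and 1:1 (SAP 6.4). High-risk non-Hispanic/Latino Caucasian sample: 2,940 expected, 2,346 required. Target 202 events, two-sided alpha 0.01, power 90%, 5-year event rates 15% and 9% (Protocol 13.3, SAP 8.0).

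**Assumption.** r, the event rate of participants relative to non-participants, is not in the documents. I take 0.5 to 2.0.

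**The plan's own figure.** With exponential times, HR = ln(0.91)/ln(0.85) = 0.580. Schoenfeld: 4 × (2.576 + 1.282)² / (ln 0.580)² gives 201 events, against 202 stated. Power at 202 events is 90.2%.

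**Imbalance.** With n participants, a = 5n/9 are on pioglitazone and b = 4n/9 on placebo; the other (N − n)/2 per arm are added to give arm sizes A and B. Taking all 300 as high-risk and in the primary population:

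- N = 2,940: a = 166.7, b = 133.3, A = 1,486.7, B = 1,453.3. Participants are 11.2% of pioglitazone and 9.2% of placebo.
- N = 2,346: A = 1,189.7, B = 1,156.3. Participants are 14.0% and 11.5%.

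**Bias with no center adjustment.** Factor on the HR = [1 + (r − 1)a/A] / [1 + (r − 1)b/B]. The last column supposes that only 252 participants are high-risk (300 × 2,940/3,500, an assumption).

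| r | N = 2,940, n = 300 | N = 2,346, n = 300 | N = 2,940, n = 252 |
|---|---|---|---|
| 0.5 | 0.989 | 0.987 | 0.991 |
| 1.0 | 1.000 | 1.000 | 1.000 |
| 1.5 | 1.010 | 1.012 | 1.008 |
| 2.0 | 1.019 | 1.022 | 1.016 |

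Example: at N = 2,940 and r = 2, 1.1121/1.0917 = 1.0187.

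**Large-sample check.** For the unstratified Cox estimate (exponential, 15% over 5 years, 12% annual dropout, 5.5 years of follow-up, N = 2,940, n = 300, r from 0.5 to 2), the factor is 0.989 to 1.018 at a true HR of 1 and 0.990 to 1.020 at a true HR of 0.6. The simple formula is adequate.

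**Against sampling error.** SE(log HR) = 2/√202 = 0.141. ln(1.0187)/0.141 = 0.13 SE (N = 2,940); ln(1.0222)/0.141 = 0.16 SE (N = 2,346). At 66 events SE = 2/√66 = 0.246, so the same shifts are 0.08 and 0.09 SE at the futility analysis.

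**Operating characteristics.** Shifting the test statistic by these amounts keeps two-sided type I error between 0.0100 and 0.0109. The design HR of 0.580 would appear as 0.573 to 0.593. Power at 202 events, 90.2% without bias, would be 87.7% (N = 2,940) or 87.2% (N = 2,346) at r = 2, and 91.4% or 91.7% at r = 0.5.

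**Cost of analysing by stratum.** Overall allocation to pioglitazone is 50.6% to 50.7%. Required events are 201 to 202 and power at 202 events stays 90.2%.

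**The case against.** The strongest reply is that this changes no plausible decision. The largest figures assume no center adjustment and all 300 participants in the primary population. The primary model does adjust for center, age, gender and education, and SAP 6.4 expects some low-risk subjects in the substudy. With 252 high-risk participants and N = 2,940 the worst case is ln(1.016)/0.141 = 0.11 SE. Nothing in the documents shows that participation is prognostic, and the range for r has no source. All of that stands, and it is why the point is minor. The range is also not a hard limit: at r = 3 the factor would be 1.034 to 1.040 and type I error 0.012 to 0.013.

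A second reply is sparse data. At equal event rates, participants would supply about 66 × 300/2,940 = 7 events at the futility analysis and 202 × 300/2,940 = 21 at the end, so one sensitivity analysis might be enough. The counts are right, but a single binary term does not strain either analysis. Crossing participation with gender arises only in the two supportive rank tests, which are not among the analyses listed for the futility look.

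Protocol 13.1.3 does foresee an investigation of covariates, but that is not a commitment to analyse by this stratum.

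**Conclusion.** The point holds, at minor severity. The plan randomises by vMRI participation with a different ratio in each stratum, and no visible primary, sensitivity or key secondary efficacy model uses it. For r from 0.5 to 2, and with no credit for the center term, the bias on the hazard ratio is about 2% or less in either direction: at most 0.13 SE with 2,940 high-risk subjects and 0.16 SE with 2,346 on the simple formula. It is zero if participation is not prognostic.

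The figures rest on the assumed r and on all participants being in the primary population. The center term and any low-risk participants would bring them down. No size has been worked out for the key secondary endpoints. The case for changing the plan is that analysing by the stated stratum settles the question at almost no cost.

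**What to change.** - Add vMRI participation (yes/no) to the primary efficacy Cox model, as a STRATA factor or a covariate. State that this carries into the alternative event-time efficacy analyses and the futility Cox model.
- Add it as a stratum alongside gender in the efficacy ICLIFETEST and LIFETEST analyses.
- Add it as a fixed effect in both key secondary treatment MMRMs.
- In Protocol 6.1, cross-reference the 5:4 ratio in Appendix H so that the two passages are reconciled.

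The cost is one binary term (1 df) in existing code, one line in the SAP and one cross-reference in the protocol. The event target and sample size do not change. The SAP change should be made before unblinding.
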